#### 1.4 Summarized risk-benefit assessment

ALS is a devastating disease which dramatically reduces the life expectancy and physical wellbeing of the patient. The potential risks of every treatment of ALS must be seen against this background.

Rasagiline is approved for the treatment of Parkinson's disease by the FDA and the EMA, hence the safety profile of rasagiline in humans is well-known. In patients with Parkinson's disease it was possible to show a disease-modifying effect by rasagiline (ADAGIO trial) [6]. Therefore it is considered justified and safe to assess the effect of rasagiline in patients with the neurodegenerative disease ALS.

Placebo as comparator is acceptable in this case since both placebo and rasagiline are given as add-on to the standard therapy riluzole.

A direct interaction of the two substances Rasagilin and Riluzol with adverse effects is not expected due to the different mechanism of action. Rasagiline is a substance presumably reducing oxidative stress by inhibition of monoamine oxidase B (MAO-B) [13]. However, neuroprotection with rasagiline has also been linked to its effects on preserving mitochondrial membrane potential [14]. The mechanism of action of riluzole is thought to be related to its stabilizing effect on sodium channels and the resulting reduction of presynaptic glutamate release [15]. The substance could be indicated as an antiglutamatergic drug to prevent the toxic effects of glutamate on motoneurones.

The neuroprotective effect of riluzole – the standard therapy for patients with ALS – could be increased by the neuroprotective effect of rasagiline. Therefore a stronger effect on the course of the disease in ALS patients is expected. The investigator will be informed about any relevant or new finding including AEs relating to treatment with the investigational medicinal product.

Evaluations which will be performed at the study visits comply with the routine assessments for ALS patients, except that there is higher frequency of performance. Routine assessments for ALS patients are usually performed approximately twice a year.

# 2 TRIAL OBJECTIVES

The purpose of this trial is to assess the efficacy of rasagiline (1mg/day) as add-on therapy to the standard therapy with riluzole in patients with ALS compared to placebo in terms of survival.

### 2.1 Primary objective

The primary objective of the trial is to investigate the survival time (the time from randomization until death or end of the trial) compared between control group and experimental group.

## 2.2 Secondary objectives

The secondary objectives of the trial are to assess:

- Change of total score of ALS Functional Rating Scale Revised (ALSFRS-R) [10]
- Change in individual Quality of Life (SEIQoL [11], Schedule for the Evaluation of Individual Quality of Life)
- Change of the slow vital capacity (sVC)

## 2.3 Assessment of Safety

Assessment of clinical tolerability and safety will be performed by comparison of vital signs, adverse events terms and incidence, and clinical laboratory values across both treatment groups.

## 3 TRIAL DESIGN

This is a prospective, multicenter, randomized, stratified, parallel-group, double-blind trial comparing placebo with 1 mg/d rasagiline as add-on therapy to 100 mg riluzole in amyotrophic lateral sclerosis (ALS) in 250 enrolled patients. For entry, the El Escorial Criteria for the diagnosis of ALS will be used. The patients have to be stable on riluzole at least 4 weeks prior to randomization. After patients are screened for inclusion and exclusion criteria, they will be randomly assigned to treatment with either placebo or 1 mg/d rasagiline according to their stratum (bulbar onset vs. spinal onset). The trial requires an initial screening visit (V0), one baseline visit (V1), 3 subsequent control visits (V2 – V4), a final visit (V5) and four telephone contacts (T1 – T4). The population consists of 250 enrolled ALS patients as defined by the El Escorial criteria (revised version). 125 patients will be randomized to treatment with 1 mg/d rasagiline and 125 patients to treatment with placebo, respectively.

The gender distribution for ALS is in favor for men (2 men in 1 woman). There are no specific requirements concerning the gender distribution within this trial as there are no differences in the course of disease. This is a multicenter study including about 15 sites in Germany. Each trial site will recruit 10 to 30 patients.

## 3.1 Trial duration and schedule

The estimated duration of the whole trial will be about 36 months: 6 months for recruitment, 18 months for the treatment period and 12 months for cleaning the data, carrying out statistical analyzes, and writing the final study report. The actual overall trial duration or patient recruitment period may vary from this estimate.

The trial duration for each patient is expected to be up to 1 month for screening and 18 months for the treatment period.

The estimated time from first patient in to last patient out will be 24 months. Recruitment of patients will start in Q1, 2013, so the anticipated end of trial of the last patient will be in Q1 2015.

## 3.2 Number of patients

It is planned to enroll 250 patients in the clinical trial, i.e. 125 patients per treatment group.

A previous study [GERP ALS-Study; 12] showed a drop-out rate of about 15 %, screening failure was observed in about 10 %. Thus, in total 250 patients have to be allocated (with consideration of a drop-out rate) and a total number of 278 patients have to be assessed for eligibility.

Recruitment and treatment of patients is expected to be performed in about 15 trial centers.

## 3.3 Primary endpoint

The primary endpoint is the time to death. Mortality is exclusively defined as death.

## 3.4 Secondary endpoints

- Change of total score of ALS Functional Rating Scale Revised (ALSFRS-R)
- Change in individual Quality of Life (SEIQoL, Schedule for the Evaluation of Individual Quality of Life)
- Change of the slow vital capacity (sVC)

## 3.5 Safety variables

Safety and tolerability of rasagiline will be investigated using the following parameters as vital signs, safety laboratory parameters, terms and frequencies of adverse and serious adverse events.

## 3.6 Measures taken to minimize/avoid bias

#### 3.6.1 Randomization

This trial has two parallel groups (rasagiline versus placebo as add-on to standard treatment with riluzole), is randomized, and treatment groups are completely masked (double-blind trial). The randomization will be performed stratified according to bulbar onset or spinal onset of the disease, and separate for each trial center.

At the screening visit (V0), each patient will receive the next consecutive screening number.

At the randomization visit (V1), each patient eligible for study participation will receive the next consecutive randomization/patient number according to his stratum (bulbar onset vs. spinal onset) from a block of randomization numbers per site. Patients will be assigned to the bulbar or spinal stratum according to the location of the earliest experienced ALS symptom (defined by the first muscle weakness, or in the case of bulbar onset, by the presence of dysarthria and/or dysphagia). In the case of a patient with simultaneous onset of spinal and bulbar symptoms, onset will be defined as bulbar. Cervical and respiratory onsets are stratified to the spinal-onset stratum. This stratum assignment must be consistent with the diagnosis and clinical assessment (i.e., maximum score on bulbar scale and low score on manual muscle testing would contradict the assignment to bulbar stratum). The randomization list will be generated by the Institute of Epidemiology and

Medical Biometry Ulm University, Germany, using a validated system, which involves a pseudorandom number generator to ensure that the resulting treatment sequence will be both reproducible and non-predictable. Study medication will be packed by TEVA Pharma GmbH and blinded by the Pharmacy of the University Hospital Ulm, Germany, according to the randomization list. Each patient medication bottle will be sent together with the sealed unblinding codes to the sites. The investigator at the site takes care that each patient will be provided with the study medication box of the correct randomization number.

The randomization list will be kept in safe and confidential custody at Pharmacy of the University Hospital Ulm, Germany.

### 3.6.2 Blinding

Blinding of the investigator and patient is achieved by providing rasagiline and matching placebo tablets.

Together with the trial medication the investigator will receive a set of sealed envelopes, one for each randomization number. These envelopes contain information on the patient's trial medication and are to be opened only under circumstances in which it is medically imperative for diagnostic or therapeutic decisions to know what the patient is receiving. Date and reason for opening of a sealed envelope must be documented by the investigator or an authorized person on the open envelope, on the CRF and on the medical record of the patient. In either case before unblinding, the investigator should attempt to consult the coordinating investigator (LKP). The randomization envelopes are not to be opened by the investigator at the end of the trial. All envelopes will be checked and collected by the monitor at the end of the trial.

## 3.7 Selection and withdrawal of patients

No patient will be allowed to enroll in this trial more than once.

#### 3.7.1 Inclusion criteria

Patients meeting all of the following criteria will be considered for admission to the trial:

- Possible, probable (clinically or laboratory) or definite ALS according to the revised version of the El Escorial World Federation of Neurology criteria
- Disease duration more than 6 months and less than 3 years (inclusive). Disease onset defined as date of first muscle weakness, excluding fasciculations and cramps
- Vital capacity more than 50% of normal (slow vital capacity; best of three measurements)
- Age: ≥ 18 years
- Continuously treated with 100 mg riluzole for at least four weeks
- Capable of thoroughly understanding all information given and giving full informed consent according to GCP
- Women of childbearing age must be non-lactating and surgically sterile or using a highly
  effective method of birth control and have a negative pregnancy test. Acceptable methods of
  birth control with a low failure rate i.e. less than 1% per year) when used consistently and
  correct are such as implants, injectables, combined oral contraceptives, hormonal intrauterine
  devices (IUDs), or double-barrier methods (condom or diaphragm with spermicidal agent or
  IUD), sexual abstinence or vasectomized partner

## 3.7.2 Exclusion criteria

Patients presenting with any of the following criteria will not be included in the trial:

- Previous participation in another clinical study within the preceding 12 weeks
- Tracheostomy or assisted ventilation of any type during the preceding three months
- Gastrostomy
- Any medical condition known to have an association with motor neuron dysfunction which might confound or obscure the diagnosis of ALS
- Presence of any concomitant life-threatening disease or impairment likely to interfere with functional assessment
- Patients on sympathomimetic agents. This includes pseudoephedrine, phenylephrine, phenylpropanolamine, and ephedrine.
- Patients on analgesics with serotoninergic properties such as meperidine, tramadol, methadone and propoxyphen.
- Patients on serotonin reuptake inhibitors (SSRIs). This includes fluoxetine or fluvoxamine.
- Patients on serotonin noradrenalin reuptake-inhibitors (SNRIs) and patients on tricyclic and tetracyclic antidepressants
- Patients on dextromethorphan, St. John's wort, cyclobenzaprine or other MAO inhibitors (selective or non-selective)
- Confirmed hepatic insufficiency or abnormal liver function (ASAT and/or ALAT greater than 3 times the upper limit of the normal range)
- Renal insufficiency (serum creatinine more than 2.26 mg/dL)
- Evidence of major psychiatric disorder or clinically evident dementia precluding evaluation of symptoms
- Known hypersensitivity to any component of the study drug
- Liable to be not cooperative or comply with the trial requirements (as assessed by the investigator), or unable to be reached in the case of emergency
- Female with childbearing potential, if no adequate contraceptive measures are used
- Pregnancy or breast-feeding females

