#### *4.1.2 Therapeutic effects*

Rasagiline is a selective and potent irreversible monoaminooxidase (MAO)-B inhibitor. The precise mechanisms of action of rasagiline are unknown. One mechanism is believed to be related to its MAO-B inhibitory activity, which causes an increase in extracellular levels of dopamine in the striatum. The elevated dopamine level and subsequent increased dopaminergic activity are likely to mediate rasagiline's beneficial effects seen in models of dopaminergic motor dysfunction.

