## 4.2 Not permitted medication

The following concomitant treatments are not permitted during the trial: (Contraindications for rasagiline)

- Meperidine, tramadol, methadone or propoxyphene
- Dextromethorphan, St. John's wort or cyclobenzaprine
- Sympathomimetic amines, including amphetamines as well as cold products and weightreducing preparations that contain vasoconstrictors (e.g., pseudoephedrine, phenylephrine and ephedrine).
- Serotonin reuptake inhibitors (SSRIs), including fluoxetine or fluvoxamine.
- Serotonin noradrenalin reuptake-inhibitors (SNRIs)
- Tricyclic and tetracyclic antidepressants
- Other MAO inhibitors (selective or non-selective)

Surgery: As with other MAO inhibitors, patients taking rasagiline should not undergo elective surgery requiring general anesthesia. Also, they should not be given local anesthesia containing cocaine or sympathomimetic vasoconstrictors. Rasagiline should be discontinued at least 14 days prior to elective surgery. If surgery is necessary sooner, benzodiazepines, mivacurium, fentanyl, morphine, and codeine may be used cautiously.

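### The exclusion of patients on other MAO inhibitors sets no minimum time since the last dose before the first rasagiline tablet at V1

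*Protocol*

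**What the plan says.** Section 3.7.2 has five drug exclusions, each worded in terms of patients who are *on* a drug or class. The one that matters here is "Patients on dextromethorphan, St. John's wort, cyclobenzaprine or other MAO inhibitors (selective or non-selective"). None of the five gives a time since last dose, and the legible part of the matching synopsis bullet gives none either.

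Two other items in the same list do look back: "Previous participation in another clinical study within the preceding 12 weeks" and "Tracheostomy or assisted ventilation of any type during the preceding three months".

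Section 4.2 covers the same drugs under the wording "The following concomitant treatments are not permitted during the trial: (Contraindications for rasagiline"). It ends with a surgery precaution: "As with other MAO inhibitors, patients taking rasagiline should not undergo elective surgery requiring general anesthesia", and then "Rasagiline should be discontinued at least 14 days prior to elective surgery".

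On timing, section 5.1 places V1 within 4 weeks of screening (V0), states no minimum gap, and has study medication handed out at V1. The trial schedule checks the inclusion and exclusion criteria at both V0 and V1.

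**The concern.** The purpose of this exclusion is to keep rasagiline from being added to the effect of another MAO inhibitor. A criterion about current use does that only if the effect ends when the tablets end. For MAO inhibition the protocol indicates otherwise. Section 4.1.2 states: "Rasagiline is a selective and potent irreversible monoaminooxidase (MAO)-B inhibitor". Section 4.2 advises two weeks off rasagiline before elective surgery. Section 4.1.5 advises tyramine restriction for several weeks after an overdose.

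The stake is patient safety at the first dose. Section 4.1.3 warns of hypertensive crisis and loss of MAO-B selectivity above the recommended dose, and section 4.1.5 lists hypertensive crisis and serotonin syndrome among the reported signs of overdose. A patient with residual inhibition from another MAO inhibitor who then starts rasagiline is the case the exclusion was written to prevent.

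**Working it through.** The protocol gives no figure to reproduce. The check has two parts: whether any provision supplies a washout, and how short the drug-free time can be as written.

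**Provisions that might close the gap**

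- *Meaning of on.* Where past exposure is meant to count, the same list says so (12 weeks, three months). The drug items say nothing, so current use is the natural reading.
- *Section 4.2.* It bars the drugs during the trial. Use that ended before V0 is outside it.
- *Check at V1.* It applies the same criterion, so it asks again about current use.
- *Section 6.3.2.* The only prior treatment it deals with is riluzole. Otherwise it covers treatments given on entry or during the trial.
- *Medical history at V0 and section 6.3.1.* These may show why a drug was taken. Neither asks for a last-dose date or attaches an eligibility consequence to one.
- *Section 4.1.3.* Investigators are to receive updated versions of the SmPC, but no section makes an SmPC interval an entry condition.

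None of these sets a minimum drug-free time.

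**Drug-free time at V1**

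Let d be the days from last dose to V0 and g the days from V0 to V1.

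Time off drug at V1 = d + g.

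Inputs: g is at most 28 (4 weeks, section 5.1) with no stated minimum. I assume g is at least 3, to allow for the V0 laboratory results. The reference is 14 days, borrowed from the surgery precaution in section 4.2. The interval is short of it when d + g < 14, that is, when g ≤ 13 − d.

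| d | Time off at g = 3 | Time off at g = 28 | Short of 14 days when |
|---|---|---|---|
| 1 | 1 + 3 = 4 days | 1 + 28 = 29 days | g ≤ 12 |
| 7 | 7 + 3 = 10 days | 7 + 28 = 35 days | g ≤ 6 |
| 10 | 10 + 3 = 13 days | 10 + 28 = 38 days | g ≤ 3 |

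With g at least 3, a shortfall needs d + 3 < 14, so a last dose no more than 10 days before V0. Without that assumption (g = 0) the limit is 13 days.

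**Does a 14-day rule fit the schedule?** It needs g ≥ 14 − d. In the tightest case, d = 1, V1 must fall on day 13 or later after V0, and days 13 to 28 are available. So a 14-day rule always fits the existing window. A longer SmPC interval of L days fits if L ≤ 28 + d.

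**The case against.** The strongest reply is that the protocol nowhere says another MAO inhibitor needs a washout before rasagiline. The 14 days concerns stopping rasagiline, before surgery, and is worded as a recommendation; where surgery is needed sooner, section 4.2 allows certain agents with caution. The comparison with other MAO inhibitors opens the sentence on avoiding elective surgery, while the 14-day sentence names rasagiline alone. Irreversibility is stated for rasagiline, not for whatever drug the patient stopped. All of this stands, and it makes the 14 days an analogy. It does not remove the gap: the protocol treats this type of effect as persisting, yet the rule meant to prevent overlap ignores recent use.

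The two look-back items are not drug washouts. That is also true. They show only that the list states a period where past exposure counts.

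Investigators are told these drugs are contraindicated, take a detailed history and receive the SmPC. Many would wait. But an entry condition applied across about 15 sites should not depend on that.

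Three stronger readings are tempting and are not supported:

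- *All five drug exclusions need a washout.* None of the five has an interval, but only for MAO inhibition does the protocol give evidence of a lasting effect. For the other four items, and for dextromethorphan, St. John's wort and cyclobenzaprine in the fifth, it gives no basis for any length.
- *Use between V0 and V1 slips through.* This is largely covered. A patient on the drug at V0 meets the exclusion there. A patient who starts later falls under section 4.2 if screening counts as part of the trial, as section 3.1 suggests: "The trial duration for each patient is expected to be up to 1 month for screening and 18 months for the treatment period". Changes in concomitant medication are also documented at V1, where the criteria are checked again.
- *The efficacy result is at risk.* Nothing in the sample size or the primary log-rank comparison depends on this criterion.

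**Conclusion.** The point holds for other MAO inhibitors whose use ended before V0. As written, such a patient is eligible however recent the last dose, and the only drug-free time before study drug is whatever the visit dates happen to give. For a last dose the day before V0, that is 4 to 29 days if V1 falls 3 to 28 days after V0, and under 14 days whenever V1 is 12 days or less after V0.

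This rests on reading *on* as current use, on the assumed 3-day minimum, and on the 14 days as a borrowed yardstick. With 125 of 250 patients allocated to rasagiline, an affected patient has a 1 in 2 chance of receiving the active drug. The protocol gives no figure for MAO inhibitor use in this population, so the number affected cannot be calculated; my judgement is that it is small. It is a safety defect in a stated eligibility rule, worth correcting because the remedy is simple, and it has no bearing on the sample size or the primary analysis.

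**What to change.** In section 3.7.2 and the matching synopsis bullet, exclude patients who are taking another MAO inhibitor, selective or non-selective, or who took one within 14 days before V1, or within the interval in the current SmPC if that is longer. Confirm this at V1 before dispensing, and record the drug and its last-dose date; section 6.3.2 is the natural place for that instruction.

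For the other four drug exclusions and the remaining drugs in the fifth, check the current SmPC and add an interval only where it states one.

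The cost is one reworded criterion in two places, one check at V1 and one date field in the eCRF. For a few patients V1 is booked later within the existing 4 weeks. The 14-day rule needs no re-screening, which matters because section 3.7 bars enrolling twice and section 7.2 links enrolment to signed consent. Only an SmPC interval too long for the window would lead to exclusion.

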#### 3.7.3 Withdrawal criteria

Patients can withdraw their consent at their own request without given reasons at all times during the trial. This should be without disadvantages for the patient.

Whenever possible, all patients prematurely discontinuing study medication should perform an early termination visit including the same evaluations as scheduled for visit V5. The reason(s) for premature cessation of a patient's participation during the trial, other than death, should be specified on the case report form.

Study treatment may be stopped prematurely if any of the following events occur, according to the judgment of the investigator:

• Significant intolerance of the study medication, or significant clinical or laboratory findings, e.g. increase in ASAT or ALAT >3 times the upper limit of normal

- Significant intercurrent illness or emergency situation requiring cessation of the study
- The patient wishes to terminate his/her participation in the study
- Investigator judgment that it is in the best interest of the patient
- Failure to comply with the investigational procedures
- Pregnancy
- Technical reasons (change of physician, change of address of volunteer/patient)

Patients who have started double-blind treatment will not be replaced.

For any patient prematurely discontinuing the study, the investigator must:

- Recover all the treatment units given to the patients
- In as far as possible, carry out all the examinations and tests planned for the final visit after withdrawal of the patient from the study
- Fill in the corresponding pages of the case report form, specifying the date and reason for premature discontinuation
- When applicable, ask the patient the reason of his/her Informed Consent withdrawal while fully respecting the patient's rights
- Where possible prescribe a visit 2 weeks after withdrawal in order to control and document any change in the patient's clinical status. If a serious adverse event occurs, the Responsible Nominated Safety Contact must be informed according to the procedures described in section 6.2.2.5. "Immediate reporting of SAEs by investigator".
- All ongoing serious adverse events of withdrawn patients have to be followed up until no more signs and symptoms are verifiable or the investigator has assessed its sequelae, even after the end of the trial.

